6.15.3.1. Special Safety Topics Including Adverse Events of Special Interest

Safety information on special topics including AESI will be presented by treatment group and by study period. [Table RHCF.6.7](#) provides the definitions/derivations and analyses methods (including analyses, summaries, and by-patient listings) of special safety topics including AESIs.

Potential AESIs will be identified by a standardized MedDRA query (SMQ) or a Lilly-defined MedDRA PT listing. Preferred terms within an SMQ will be classified as broad or narrow. In

the Lilly-defined MedDRA PT listings, Lilly has provided the broad and narrow classification. The Lilly-defined broad terms are for a more sensitive search of potential events of interest and the Lilly-defined narrow terms are for a more specific search. Therefore, the summaries will include the classifications of broad term (same as pooling narrow and broad terms together) and narrow term. In the event that the listing of terms or analysis changes for a special safety topic, it will be documented in the program safety analysis plan (PSAP), which will supersede this document; it will not warrant an amendment to the individual study SAP.

Table RHCF.6.7. Definitions and Analyses of Special Safety Topics

Special Safety Topic	Definition/Derivation	Analysis/Summary/Listing
Hepatic	
Hepatic AE analysis will include events that are potentially drug-related hepatic disorders by using the MedDRA PTs contained in any of the following SMQ or sub-SMQ as defined in MedDRA:
 
 • Broad and narrow terms in the Liver-related investigations, signs and symptoms (20000008) • Broad and narrow terms in the Cholestasis and jaundice of hepatic origin (20000009) • Broad and narrow terms in the Hepatitis, non-infectious (20000010) • Broad and narrow terms in the Hepatic failure, fibrosis and cirrhosis and other liver damage (20000013) • Narrow terms in the Liver-related coagulation and bleeding disturbances (20000015) 	
Open-Label Treatment Period (Safety Population): TEAE by PT within SMQ or sub-SMQ

	
Elevations in hepatic laboratory tests (ALT, AST, ALP, total bilirubin) using Performing Laboratory Reference Ranges are defined as:
 
 • Include scheduled visits, unscheduled visits, and repeat measurements. • ALT or AST: maximum post-baseline measurement ≥ 3 times ($3\times$), 5 times ($5\times$), 10 times ($10\times$), and 20 times ($20\times$) the Performing Lab ULN for all patients with a post-baseline value. 
 ○ The analysis of $3\times$ ULN will contain 4 subsets: patients whose non-missing maximum baseline value is $\leq 1\times$ ULN, patients whose maximum baseline is $>1\times$ ULN but $<3\times$ ULN, patients whose maximum baseline value is $\geq 3\times$ ULN, and patients whose baseline values are missing. ○ The analysis of $5\times$ ULN will contain 5 subsets: patients whose non-missing maximum baseline value is $\leq 1\times$ ULN, patients whose maximum baseline is $>1\times$ ULN but $<3\times$ ULN, patients whose maximum baseline is $\geq 3\times$ ULN but $<5\times$ ULN, patients whose maximum baseline value is $\geq 5\times$ ULN, and patients whose baseline values are missing. ○ The analysis of $10\times$ ULN will contain 6 subsets: patients whose non-missing maximum baseline value is $\leq 1\times$ ULN, patients whose maximum baseline is $>1\times$ ULN but $<3\times$ ULN, patients whose maximum baseline is $\geq 3\times$ ULN but $<5\times$ ULN, patients whose maximum baseline is $\geq 5\times$ ULN but $<10\times$ ULN, patients whose maximum baseline value is $\geq 10\times$ ULN, and patients whose baseline values are missing. ○ The analysis of $20\times$ ULN will contain 7 subsets: patients whose non-missing maximum baseline value is $\leq 1\times$ ULN, patients whose maximum baseline is $>1\times$ ULN but $<3\times$ ULN, patients whose maximum baseline is $\geq 3\times$ ULN but $<5\times$ ULN, patients whose maximum baseline is $\geq 5\times$ ULN but $<10\times$ ULN, patients whose maximum baseline is $\geq 10\times$ ULN but $<20\times$ ULN, patients whose maximum baseline value is $\geq 20\times$ ULN, and patients whose baseline values are missing. ○ The analysis of $3\times$ ULN will contain 4 subsets: patients whose non-missing maximum baseline value is $\leq 1\times$ ULN, $>1\times$ ULN to $<3\times$ ULN, $\geq 3\times$ ULN, or missing. 	
Open-Label Treatment Period (Safety Population): Elevations in hepatic laboratory tests: maximum baseline category to abnormal maximum post-baseline category


Special Safety Topic	Definition/Derivation	Analysis/Summary/Listing
	
 ○ The analysis of 5× ULN will contain 5 subsets: patients whose non-missing maximum baseline value is ≤1× ULN, >1× ULN to <3× ULN, ≥3× ULN to <5× ULN, ≥5× ULN, or missing. ○ The analysis of 10× ULN will contain 6 subsets: patients whose non-missing maximum baseline value is ≤1× ULN, >1×ULN to <3× ULN, ≥3× ULN to <5× ULN, ≥5× ULN to <10× ULN, ≥10× ULN, or missing. ○ The analysis of 20× ULN will contain 7 subsets: patients whose non-missing maximum baseline value is ≤1×ULN, >1×ULN to <3× ULN, ≥3× ULN to <5× ULN, ≥5× ULN to <10× ULN, ≥10× ULN to <20× ULN, ≥20× ULN, or missing. ● Total bilirubin: The number and percentages of patients with a total bilirubin measurement ≥1.5 times (1.5×), and ≥2 times (2×) the Performing Lab ULN during the treatment period will be summarized for all patients with a post-baseline value. 
 ○ The analysis of 1.5× ULN will contain 4 subsets: patients whose non-missing maximum baseline value is ≤1× ULN, patients whose maximum baseline is >1× ULN but <1.5× ULN, patients whose maximum baseline value is ≥1.5× ULN, and patients whose baseline values are missing. ○ The analysis of 2× ULN will contain 5 subsets: patients whose non-missing maximum baseline value is ≤1× ULN, patients whose maximum baseline is >1× ULN but <1.5× ULN, patients whose maximum baseline is ≥1.5× ULN but <2× ULN, patients whose maximum baseline value is ≥2× ULN, and patients whose baseline values are missing. ● ALP: The number and percentages of patients with an ALP measurement >1.5× the Performing Lab ULN during the treatment period will be summarized for all patients with a post-baseline value, and divided into 4 subsets: patients whose non-missing maximum baseline value is ≤1× ULN, patients whose maximum baseline is >1× ULN but ≤1.5× ULN, patients whose maximum baseline value is >1.5× ULN, and patients whose baseline values are missing. ● The number and percentages of patients meeting the following elevated hepatic criteria: maximum ALT ≥3× ULN and maximum Total Bilirubin ≥2× ULN during the treatment period will be summarized. 	
	
Shift for ALT, AST, and total bilirubin from maximum baseline to maximum post-baseline will be produced with the requirements using Performing Lab Reference Ranges:
 
 ● Include scheduled visits, unscheduled visits, and repeat measurements. ● Use the maximum non-missing value in the baseline period. ● Use the maximum non-missing post-baseline value within each study period. ● Categories are: 	
Open-Label Treatment Period (Safety Population): Shifts from maximum baseline to maximum post-baseline category

Special Safety Topic	Definition/Derivation	Analysis/Summary/Listing
	
 ○ ALT: $\leq 1 \times \text{ULN}$, >1 to $<3 \times \text{ULN}$, ≥ 3 to $<5 \times \text{ULN}$, ≥ 5 to $<10 \times \text{ULN}$, ≥ 10 to $<20 \times \text{ULN}$, and $\geq 20 \times \text{ULN}$ ○ AST: $\leq 1 \times \text{ULN}$, >1 to $<3 \times \text{ULN}$, ≥ 3 to $<5 \times \text{ULN}$, ≥ 5 to $<10 \times \text{ULN}$, ≥ 10 to $<20 \times \text{ULN}$, and $\geq 20 \times \text{ULN}$ ○ Total bilirubin: $\leq 1 \times \text{ULN}$, >1 to $<1.5 \times \text{ULN}$, ≥ 1.5 to $<2 \times \text{ULN}$, and $\geq 2 \times \text{ULN}$ ○ ALP: $\leq 1 \times \text{ULN}$, >1 to $\leq 1.5 \times \text{ULN}$, and $>1.5 \times \text{ULN}$ • With additional categories: 
 ○ Decreased: post-baseline category $<$ baseline category ○ Increased: post-baseline category $>$ baseline category ○ Same: post-baseline category = baseline category 
Elevated hepatic criteria: maximum ALT $\geq 3 \times \text{ULN}$ and maximum total bilirubin $\geq 2 \times \text{ULN}$. Listing of patients who meet any of the following criteria:
 
 • Elevated hepatic criteria: defined as maximum ALT $\geq 3 \times \text{ULN}$, maximum total bilirubin $\geq 2 \times \text{ULN}$ • An ALT or AST $\geq 3 \times \text{ULN}$ • An ALP $\geq 1.5 \times \text{ULN}$ • A total bilirubin $\geq 2 \times \text{ULN}$ 
The listing will include patient demographics, concomitant medications, ALT/AST/ALP/total bilirubin/GGT by visit, treatment start and stop dates, and reason for treatment discontinuation
 
eDISH plot: Use maximum ALT measurement and maximum total bilirubin measurement with patients having at least 1 post-baseline ALT and total bilirubin, which contributes 1 point to the plot. The measurements do not need to be taken at the same blood draw.
	
Analysis/Summary/Listing
 
Open-Label Treatment Period (Safety Population): Elevated hepatic criteria
 
Open-Label Treatment Period (Safety Population): eDISH plot (to be prepared in spotfire)

Cytopenias	
Cytopenias are defined using the PTs from the following 2 sub-SMQs of the Haematopoietic cytopenias SMQ (20000027) as specified in MedDRA:
 
 • Broad and narrow terms in the Haematopoietic leukopenia (20000030) • Broad and narrow terms in the Haematopoietic thrombocytopenia (20000031) 	
Open-Label Treatment Period (Safety Population): TEAE by PT within sub-SMQ

Infections	
Infections are events including all infections (defined using all the MedDRA PTs from the Infections and infestations SOC), serious infections, potential opportunistic infections, and infections resulting in anti-infective medication administration (i.e., antibacterial, antiviral, antifungal, antiparasitic treatment.). The relationship between TEAE infections and other clinical, laboratory, and hematology parameters will be examined using Spotfire tool.
	
Open-Label Treatment Period (Safety Population): TEAE by PT TEAE by maximum severity by PT* SAE by PT*

Special Safety Topic	Definition/Derivation	Analysis/Summary/Listing
		
AEs leading to discontinuation of study drug*
 
*Included in overall TEAE by maximum severity, SAE and DCAE.

	
Anti-infective medications are defined in Appendix 8 including antibiotics, antifungals, antivirals, or antiprotozoals.
	
	
The OIs are defined in Appendix 9. This list contain PTs as contained within Categories (narrow or broad) from the Infections and Infestations SOC and from the Investigations SOC that can assist in identifying potential OIs. The narrow terms are considered OIs unless medical review determines that the reported term is not consistent with the patient’s clinical history/presentation/course. Medical review of broad terms is needed for final determination of patients meeting the program definition of OIs.
 
The number and percentage of patients with TEAEs that represent potential OIs and as potential OIs will be summarized by treatment group using MedDRA PT nested within categories. Events will be ordered by decreasing frequency in the ixekizumab group nested within categories.
	
Open-Label Treatment Period (Safety Population): TEAE of OIs by PT within category
 
Listing: TEAE of OIs

	
The duration of each common TEAE PT of Infections and narrow terms for OIs is defined as: Duration of treatment-emergent AE Infections (in weeks) = (End date of AE – Start date of AE + 1) / 7 Patients who do not have the PT will not be included in the analysis. If the TEAE has not been reported as ended by the date of completion from the study, or date of early discontinuation, it will be censored as of that date. If a patient has multiple episodes of the same TEAE, the episode with the greatest severity will be used for the duration of event calculation. If a patient has multiple episodes of the same TEAE with the same severity, the episode with the longest duration will be used for the duration of event calculation.
	
Open-Label Treatment Period (Safety Population): Duration of Common TEAE Duration of OIs (narrow terms) (to be prepared in spotfire) Duration of Candida infections (to be prepared in spotfire)

Special Safety Topic	Definition/Derivation	Analysis/Summary/Listing
Allergic Reactions/ Hypersensitivities	
Allergic reactions/hypersensitivity events will be categorized as either anaphylaxis or non-anaphylaxis events (these will refer to events that are not localized to the site of injection) and summarized separately. Allergic Reactions/Hypersensitivity Events, Anaphylaxis: Anaphylaxis has been broadly defined as “a serious allergic reaction that is rapid in onset and may cause death” (Sampson et al. 2006). Identification of cases of potential anaphylaxis from the clinical trial data involves two screening criteria:
 
 1) designed to specifically identify cases (following Criterion 1) based on narrow terms from the MedDRA SMQ for anaphylactic reaction (20000021). Criterion 1 for anaphylaxis is defined by the presence of a TEAE based on the following MedDRA PTs from the anaphylactic reaction SMQ: 
 • Anaphylactic reaction • Anaphylactic shock • Anaphylactoid reaction • Anaphylactoid shock • Kounis Syndrome • Type 1 hypersensitivity 2) to identify possible cases, following Criterion 2 as defined by Sampson et al. (2006). Criterion 2 for anaphylaxis requires having TEAEs from two or more of four categories of AEs as described by Sampson et al. (2006). Occurrence of these events should be nearly coincident; based on recording of events or CRFs. All qualifying events must be within 1 day of study drug injection. 
The 4 categories to be considered in Criterion 2 are:
 
 • Category A: Involvement of the skin-mucosal tissue • Category B: Respiratory compromise • Category C: Reduced blood pressure or associated symptoms • Category D: Persistent gastrointestinal symptoms 
The specific MedDRA PTs covered by each of these Criterion 2 categories are shown in Appendix 10. Summaries of Criterion 2 anaphylactic TEAEs will be provided by the specific combination of categories as follows:
 
 • AB: events based on meeting Category A and Category B (but no other category) • AC: events based on meeting Category A and Category C (but no other category) • AD: events based on meeting Category A and Category D (but no other category) • BC: events based on meeting Category B and Category C (but no other category) • BD: events based on meeting Category B and Category D (but no other category) • CD: events based on meeting Category C and Category D (but no other category) • ABC: events based on meeting Category A, Category B, and Category C (but no other category) • ABD: events based on meeting Category A, Category B, and Category D (but no other category) 	
Open-Label Treatment Period (Safety Population): TEAE by PT within Category TEAE by maximum severity by PT SAE by PT within Category AE leading to discontinuation of study drug within Category


Special Safety Topic	Definition/Derivation	Analysis/Summary/Listing
	
 • ACD: events based on meeting Category A, Category C, and Category D (but no other category) • BCD: events based on meeting Category B, Category C, and Category D (but no other category) • ABCD: events based on meeting each of the 4 Criterion 2 categories 
Summaries of treatment-emergent anaphylactic AEs will be provided for patients meeting each of the 2 criteria and for patients who meet either criteria overall. Separate summaries will be provided for TEAEs by maximum severity, SAEs, and AEs resulting in study drug discontinuation. Severity of treatment-emergent Criterion 2 anaphylactic AEs will be based on the maximum severity of the specific events met by the patient. Maximum severity of an (overall) treatment-emergent anaphylactic AE will be based on the maximum severity within Criterion 1 and/or Criterion 2.
 
Allergic Reactions/Hypersensitivity Events, Non-Anaphylaxis: TEAEs of allergic reaction/hypersensitivity categorized as non-anaphylaxis events are defined by the narrow terms within Hypersensitivity SMQ (20000214) excluding the PTs noted in Appendix 11 and excluding the anaphylactic events as defined above.
	

Special Safety Topic	Definition/Derivation	Analysis/Summary/Listing
Injection Site Reactions	
Injection site reaction is defined using the PTs from the MedDRA HLT of Injection site reactions as defined by MedDRA excluding the following 10 PTs:
 
 1) Embolia cutis medicamentosa 2) Injection site joint discomfort 3) Injection site joint effusion 4) Injection site joint redness 5) Injection site joint infection 6) Injection site joint inflammation 7) Injection site joint movement impairment 8) Injection site joint pain 9) Injection site joint swelling 10) Injection site joint warmth. 	
Open-Label Treatment Period (Safety Population): TEAE by PT within HLT TEAE by maximum severity by PT within HLT AE leading to discontinuation of study drug within HLT

	
The Injection Site Reaction eCRF page captures the injection site reactions identified by the investigator. Patients with TEAE of injection site reactions will be categorized into 3 groups: patients with 1 TEAE of injection site reaction event, patients with 2 or 3 events, and patients with ≥ 4 events.
 
Redness (Scored 0-4)
 
 • [0] Subject’s normal skin color, no increased redness • [1] Noticeable, but very mild redness • [2] Clearly red • [3] Bright red • [4] Dark with some scar formation 
Swelling (Scored 0-4 after running a finger over injected area)
 
 • [0] No bump • [1] Barely noticeable • [2] Clear bump but very thin • [3] Clear bump 1 mm thick • [4] Clear bump 2 mm thick or more 
Pain (including burning) (Scored 0-3)
 
 • [1] Mild • [2] Moderate • [3] Severe 	
Open-Label Treatment Period (Safety Population): TEAE identified by the investigator by PT within HLT TEAE identified by the investigator by maximum severity by PT within HLT TEAE identified by the investigator by max redness category within HLT TEAE identified by the investigator by max swelling category within HLT TEAE identified by the investigator by max pain category within HLT

Special Safety Topic	Definition/Derivation	Analysis/Summary/Listing
Cerebro-cardiovascular Events	
Cerebro-cardiovascular events will be externally adjudicated by the CEC at the Cleveland Clinic, as outlined in the Manual of Operations. The CEC will adjudicate investigator-reported events selected for adjudication and render an assessment as to whether the event represents a confirmed event (meeting the event definition with all necessary documentation), a non-event (does not meet the event definition and likely represents an alternative or nonevent diagnosis), or lacks sufficient documentation for confirmation of an event. All events which qualify for CEC adjudication will be used for the analysis of cerebro-cardiovascular events. The categories and subcategories of adjudicated events used for the analysis will include the following:
 
 • Cardiovascular 
 ○ Death (Cardiovascular) ○ MI ○ Hospitalization for Unstable Angina ○ Hospitalization for Heart Failure ○ Serious Arrhythmia ○ Hospitalization for Hypertension ○ Resuscitated Sudden Death ○ Cardiogenic Shock due to Myocardial Infarction ○ Coronary Revascularization • Neurologic 
 ○ Cerebrovascular Event: Transient Ischemic Attack or Stroke (Hemorrhagic, Ischemic, and Undetermined) • Peripheral Vascular Events 
 ○ Peripheral Arterial Event ○ Peripheral Revascularization 
Events will be analyzed using MedDRA PT nested within the CEC assessment (confirmed event, no event, or insufficient documentation for event determination) and the subcategory. Subcategories of stroke (Hemorrhagic Stroke, Ischemic Stroke, and Unknown Stroke Type) will be displayed in the analyses nested within stroke. Subcategories of Serious Arrhythmia (Atrial Arrhythmia, Ventricular Arrhythmia, Heart Block, Other, Unknown) will be displayed nested within Serious Arrhythmia.
	
Open-Label Treatment Period (Safety Population): TEAE by PT within Subcategory

MACE	
MACE (requiring adjudication as defined above) is defined as:
 
 • Vascular death (including cardiovascular and cerebro-vascular causes excluding hemorrhagic deaths outside of the central nervous system) • Non-fatal myocardial infarction 	
Open-Label Treatment Period (Safety Population): TEAE by maximum severity PT within Category

Special Safety Topic	Definition/Derivation	Analysis/Summary/Listing
	
 • Non-fatal stroke (subcategories: ischemic, hemorrhagic, unknown stroke type) 
Where,
 
 • Vascular death should be captured as an Event on Adjudication - Death eCRF page with Adjudication Death Type = “Cardiovascular.” • Non-fatal myocardial infarction should be captured as an Event on Adjudication - Cardiac Ischemic Event eCRF page with Type of Ischemic Event = “Myocardial Infarction” and the Event is NOT on Adjudication - Death eCRF page. 
Non-fatal strokes (ischemic, hemorrhagic) should be captured as an Event on Adjudication - Cerebrovascular Event eCRF page with Stroke Cerebrovascular Event Subtype in one of the following categories: hemorrhagic stroke, ischemic stroke, undetermined stroke type, and the Event is NOT on Adjudication - Death eCRF page. Subcategories of non-fatal stroke (Hemorrhagic Stroke, Ischemic Stroke, and Undetermined Stroke Type) will be displayed nested within non-fatal stroke category.
	
Malignancies	
Malignancy is defined using PTs from the Malignant or unspecified tumors SMQ as defined in MedDRA (SMQ: 20000091, which includes the sub-SMQs: (1) 20000194 [Malignant tumours], including sub-SMQs of 20000227 [Haematological malignant tumours] and 20000228 [Non-haematological malignant tumours]; (2) 20000195 [Tumours of unspecified malignancy], including sub-SMQs of 20000229 [Haematological tumours of unspecified malignancy] and 20000230 [Non-haematological tumours of unspecified malignancy]. Events will be summarized by the following categories:
 
 • NMSC 
 ○ Basal Cell Carcinoma, PTs include: 
 ▪ Basal cell carcinoma ▪ Basosquamous carcinoma ▪ Basosquamous carcinoma of skin ○ Squamous Cell Carcinoma, PTs include: 
 ▪ Squamous cell carcinoma of skin ▪ Bowen’s disease ▪ Lip squamous cell carcinoma ▪ Skin squamous cell carcinoma metastatic ▪ Keratoacanthoma • Malignancies excluding NMSC: all PTs in the Malignant or unspecified tumors SMQ excluding the 8 defined NMSC PTs. 	
Open-Label Treatment Period (Safety Population): TEAE by PT within Category

Depression	
Depression and suicide/self-injury is defined using the PTs from the Depression and suicide/self-injury SMQ as specified in MedDRA (SMQ: 20000035, which includes the sub-SMQs: 20000037
	
Open-Label Treatment Period (Safety Population):

Special Safety Topic	Definition/Derivation	Analysis/Summary/Listing
	[Suicide/self-injury] and 20000167 [Depression (excluding suicide and self-injury)]).	TEAE by PT within SMQ
IBD	IBD will be identified using the following subcategory and MedDRA PTs. The narrow terms are considered IBD. Medical reviews of patients identified with broad terms are needed for final determination of patients with IBD. IBD Specific Terms (Narrow terms) 
 • Inflammatory Bowel Disease: Inflammatory bowel disease • Crohn’s Disease: Crohn’s disease • Ulcerative Colitis: Acute hemorrhagic ulcerative colitis; Colitis ulcerative; Proctitis ulcerative IBD Non-Specific Terms: The PTs in this category are listed in Appendix 11 .	Open-Label Treatment Period (Safety Population): TEAE by PT within subcategory
ILD	ILD is defined using the following terms: 
 • Narrow terms in the Interstitial lung disease SMQ (20000042) • Additional 6 PTs from Eosinophilic pneumonia SMQ (20000157): 
 ○ Angiolymphoid hyperplasia with eosinophilia (Narrow) ○ Eosinophilic bronchitis (Narrow) ○ Hypereosinophilic syndrome (Narrow) ○ Loeffler’s syndrome (Narrow) ○ Pulmonary eosinophilia (Narrow) ○ Pulmonary vasculitis (Narrow) 	Open-Label Treatment Period (Safety Population): TEAE by PT by maximum severity by PT within interstitial lung disease

Abbreviations: AE = adverse event; AESI = adverse event of special interest; ALP = alkaline phosphatase; ALT = alanine aminotransferase; AST = aspartate aminotransferase; CEC = Central Events Committee; eCRF = electronic case report form; eDISH = Evaluation of Drug-Induced Serious Hepatotoxicity; GGT = gamma-glutamyltransferase; HLT = High Level Term; IBD = inflammatory bowel disease; ILD = Interstitial Lung Disease; ITT = intent-to-treat; MACE = Major Adverse Cerebro-Cardiovascular Events; MedDRA = Medical Dictionary for Regulatory Activities; MI = myocardial infarction; NMSC = Nonmelanoma Skin Cancer; OI = opportunistic infection; PsA = psoriatic arthritis; PT = preferred term; SAE = serious adverse event; SMQ = standardized MedDRA query; SOC = System Organ Class; TB = tuberculosis; TEAE = treatment-emergent adverse event; ULN = upper limit of normal.

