8.1. Discontinuation from Study Treatment

8.1.1. Permanent Discontinuation from Study Treatment

Discontinuation of the investigational product for abnormal liver tests **should be considered** by the investigator when a patient meets one of the following conditions after consultation with the Lilly-designated medical monitor:

- alanine aminotransferase (ALT) or aspartate aminotransferase (AST) >8X upper limit of normal (ULN)
- alanine aminotransferase or AST >5X ULN for more than 2 weeks
- alanine aminotransferase or AST >3X ULN and total bilirubin level (TBL)
 >2X ULN or prothrombin time >1.5X ULN
- alanine aminotransferase or AST >3X ULN with the appearance of fatigue, nausea, vomiting, right upper-quadrant pain or tenderness, fever, rash, and/or eosinophilia (>5%)
- alkaline phosphatase (ALP) >3X ULN
- alkaline phosphatase >2.5X ULN and TBL >2X ULN
- alkaline phosphatase >2.5X ULN with the appearance of fatigue, nausea, vomiting, right quadrant pain or tenderness, fever, rash, and/or eosinophilia (>5%)

In addition, patients will be discontinued from the investigational product in the following circumstances:

- Neutrophil (segmented) counts (see Section 9.4.5.3 for information on monitoring for neutropenia)
 - o <500 cells/uL
 - ≥500 and <1000 cells/uL (based on 2 test results; the second test performed within 1 week from knowledge of the initial result).
 - ≥1000 and <1500 cells/uL (based on 3 test results) and an infection that is not fully resolved.
 

- Total white blood cell count <2000 cells/μL.
- Lymphocyte count <500 cells/μL.
- Platelet count <50,000 cells/μL.
- Changes in blood pressure defined as sitting systolic blood pressure at ≥160 mm Hg plus ≥20 mm Hg increase from baseline (Visit 2 [Week 0]), and/or diastolic blood pressure at ≥100 mm Hg plus ≥10 mm Hg increase from baseline, that do not respond following maximal allowed intervention (see Section 9.4.5.1 for information on monitoring hypertension).

- The patient experiences a severe AE, an SAE, or a clinically significant change in a laboratory value occurs that, in the opinion of the investigator, merits the discontinuation of the investigational product and appropriate measures being taken. In this case, Lilly or its designee is to be notified immediately.
- Clinically significant systemic hypersensitivity reaction after SC administration of investigational product that does not respond to symptomatic medication or results in clinical sequelae.
- The patient becomes pregnant.

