Important Protocol Violation Category/Subcategory	Source to Identify Protocol Violation	Statistical Programming Guidance for Clinical Study Report
[48] Are currently enrolled in, or discontinued from a clinical trial involving an investigational product or nonapproved use of a drug or device within the last 4 weeks or a period of at least 5 half-lives of the last administration of the drug, whichever is longer, or are concurrently enrolled in any other type of medical research judged not to be scientifically or medically compatible with this study.	Monitor	Monitor's list
[49] Are unwilling or unable to comply with the use of a data collection device to directly record data from the patient.	Monitor	Monitor's list
Category: Study Procedures		
Sub-Category: Violation of Discontinuation Criteria		
[D1] Discontinuation of the study drug after consultation with medical monitor for abnormal liver tests, defined as having 1 of the following: ALT or AST >8× ULN ALT or AST >5× ULN for more than 2 weeks ALT or AST >3× ULN and total bilirubin level >2× ULN or prothrombin time >1.5× ULN ALT or AST >3×ULN with the appearance of fatigue, nausea, vomiting, right upper-quadrant pain or tenderness, fever, rash, and/or eosinophilia (>5%) ALP >3× ULN ALP >2.5× ULN and TBL >2× ULN ALP >2.5× ULN with the appearance of fatigue, nausea, vomiting, right quadrant pain or tenderness, fever, rash, and/or eosinophilia (>5%)	Monitor	Monitor's list

Important Protocol Violation Category/Subcategory	Source to Identify Protocol Violation	Statistical Programming Guidance for Clinical Study Report
[D2] Neutrophil (segmented) counts: <500 cells/ μ L; or \geq 500 and <1000 cells/ μ L (from 2 test results; the second test must be performed within 1 week from knowledge of the initial result); or \geq 1000 and <1500 cells/ μ L (from 3 test results) and an infection that is not fully resolved	Monitor and Stats	Monitor’s list, or, If a patient still receives study treatment after 10 days of latest dose with confirmed segmented neutrophil counts <500 cells/ μ L; \geq 500 and <1000 cells/ μ L (from a test and a re-test result; the re-test must be performed within 1 week from knowledge of the initial result); or \geq 1000 and <1500 cells/ μ L (from a test and 2 re-test results) and an infection that is not fully resolved If there are missing re-test results, use the non-missing results

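### The by-arm joint transaminase–bilirubin count and the eDISH plot in SAP Table RHCF.6.7 use ALT only, so an AST-led joint case is left out of the count

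*SAP*

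**What the plan says.** The hepatic part of SAP Table RHCF.6.7 has two outputs that combine a transaminase with bilirubin in the same patient.

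- The joint count: "maximum ALT ≥3× ULN and maximum Total Bilirubin ≥2× ULN during the treatment period will be summarized". The same ALT-based definition recurs later in the table and is the first entry condition of the by-patient listing.
- The eDISH plot: "Use maximum ALT measurement and maximum total bilirubin measurement".

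The other transaminase outputs in that table include AST.

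- Elevation summary: "Elevations in hepatic laboratory tests (ALT, AST, ALP, total bilirubin) using Performing Laboratory Reference Ranges are defined as". The ≥3×, 5×, 10× and 20× ULN cut-offs apply to ALT and to AST.
- Shift tables: "Shift for ALT, AST, and total bilirubin from maximum baseline to maximum post-baseline will be produced".
- Listing: ALT or AST at or above 3× ULN is a separate entry condition, and the columns include "ALT/AST/ALP/total bilirubin/GGT by visit".

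Outside the table, Protocol 8.1.1 has a combined liver criterion, which SAP Table RHCF.6.9 repeats as item D1: "ALT or AST >3× ULN and total bilirubin level >2× ULN or prothrombin time >1.5× ULN". Protocol 9.4.5.2 starts hepatic monitoring at ALT ≥3×, ALP ≥2× or total bilirubin ≥2× ULN and does not name AST. SAP 6.15.4 takes ALT, AST, bilirubin and ALP out of the general abnormal-laboratory analysis and refers liver-injury risk to Table RHCF.6.7. If the analysis of a special safety topic changes, SAP 6.15.3.1 says that "it will be documented in the program safety analysis plan (PSAP), which will supersede this document".

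**The concern.** AST is used wherever a transaminase is reported on its own, and is dropped at the one step where a transaminase and bilirubin are joined within a patient. No section gives a reason.

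The joint count and the eDISH plot are the only planned by-arm outputs that make this join, and no other laboratory analysis covers it. Separate AST and bilirubin tables cannot show whether the two rises belong to the same patient. If such a case is AST-led, the comparison of arms on the combined signal misses it. The reader then has to rebuild the count by arm from a listing.

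Only descriptive safety reporting is at stake. Efficacy, power and error rates are untouched.

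**Working it through.** The plan gives no figure to reproduce. The check compares the definitions, follows one patient through the outputs, and bounds the number omitted.

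**1. Definitions side by side**

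| Output or rule | Transaminase used |
|---|---|
| Joint count, Table RHCF.6.7 | ALT |
| eDISH plot, Table RHCF.6.7 | ALT |
| Elevation summary, Table RHCF.6.7 | ALT, AST |
| Shift tables, Table RHCF.6.7 | ALT, AST |
| Listing, transaminase entry condition | ALT or AST |
| Protocol 8.1.1 and SAP item D1, combined criterion | ALT or AST |
| Protocol 9.4.5.2, monitoring trigger | ALT |

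**2. One patient followed through the table.** Take maximum AST ≥3×, maximum total bilirubin ≥2× and maximum ALT <3× ULN.

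- Joint count: not counted.
- eDISH plot: shown at the raised bilirubin value, but outside the joint quadrant.
- AST elevation summary and bilirubin summary: counted in each.
- Listing: enters by two routes (AST ≥3×, bilirubin ≥2×), with values by visit.
- Protocol 8.1.1: the combined criterion is met if AST is above 3× and bilirubin above 2× ULN.

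**3. Bound on the number omitted, per arm**

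- O = omitted patients (AST ≥3×, bilirubin ≥2×, ALT <3× ULN).
- B = patients with bilirubin ≥2× ULN, from the bilirubin summary, added over its baseline subsets.
- J = patients in the ALT-based joint count.
- A = patients with AST ≥3× ULN, from the elevation summary, added over its baseline subsets.

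Every patient in J is also in B, so B − J counts those with bilirubin ≥2× who do not meet the ALT condition. Every omitted patient is among them, so O ≤ B − J. Every omitted patient also has AST ≥3×, so O ≤ A. Hence

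0 ≤ O ≤ min(B − J, A), and B = J gives O = 0.

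A must come from the elevation summary, which has an explicit missing-baseline subset. The shift tables use the maximum non-missing baseline value and list no missing-baseline category. A patient without a baseline AST could be absent from them and still be an omitted case, so O ≤ A would not be guaranteed.

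**4. Size of one case.** At the planned 275 per arm, 1/275 = 0.0036, or 0.36 percentage points.

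**The case against.** The strongest reply is that an ALT-based composite is a deliberate and defensible choice. ALT is the more liver-specific enzyme. The same joint definition appears consistently within the table, with broader single-analyte screens beside it. The ALT ≥3× and bilirubin ≥2× cut-offs match those in Protocol 9.4.5.2, which does not name AST. Protocol 8.1.1 is a rule for managing individual patients: it uses strict inequalities, adds a prothrombin-time alternative and asks only that discontinuation be considered. Nothing requires a tabulated criterion to match it. An AST-led case can also be counted from the planned listing.

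Much of this stands, and it rules out several stronger readings.

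- A reader might infer that the SAP breaches the protocol. It does not: the protocol's own liver rules differ on AST, and 8.1.1 is not an analysis definition.
- A reader might infer that AST-led cases are hidden. They are not, as step 2 of the check shows.
- A reader might infer that every other liver output includes AST. Only the transaminase outputs do. The bilirubin and ALP summaries and the MedDRA hepatic event summary do not involve AST by their nature.

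The reply does not explain why AST is included in the single-analyte outputs and omitted from the joint one. Protocol 9.4.5.2 lists single-analyte triggers and is not a joint criterion, so matching cut-offs do not supply that reason. Keeping the ALT-only row also preserves whatever was intended by it.

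**Conclusion.** The point holds as a minor, cheaply avoidable gap in a descriptive safety summary: no planned by-arm output counts an AST-led joint transaminase–bilirubin case.

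The number affected cannot be derived from the documents and may be zero. Per arm it is at most min(B − J, A), and each case is 0.36 percentage points if the arm has the planned 275 treated patients.

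The conclusion rests on Table RHCF.6.7 as written. The SAP revision history says its definitions were updated to agree with PSAP V8, which is not among the documents. If the PSAP now in force already has an ALT-or-AST joint count, the gap is closed.

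A reader might go further and conclude that the ALT axis of the eDISH plot is wrong and should be replaced. The documents do not support that. Replacement is a trade-off, because it would lose specificity and possibly comparability with other studies in the programme that plot ALT.

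**What to change.** Add one by-arm row to the hepatic part of Table RHCF.6.7: maximum (ALT or AST) ≥3× ULN with maximum total bilirubin ≥2× ULN. Keep the ALT-only row beside it. Optionally add a second eDISH plot using the higher of ALT/ULN and AST/ULN, and leave the ALT plot in place.

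The cost is one table row and, if wanted, one extra plot, from data already collected. No protocol amendment is needed. SAP 6.15.3.1 allows the change through the PSAP without amending the SAP.

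The downside is that AST is less liver-specific, so a few non-hepatic cases may enter the added row. CPK is among the planned laboratory tests (Protocol Appendix 2) and can help in judging such cases.
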